3.3 Usual Care

Primary care providers in the usual care arm will be asked to identify eligible patients from their practice and obtain informed consent for the patients to participate in the study. Aside from obtaining informed consent and completion of patient questionnaires there will be no other study specific intervention imposed on this arm. It is anticipated, that usual care will be provided according to current Canadian and international guidelines for the treatment and management of AF and represent the accepted standard care as established by the major medical specialty organizations dealing with AF management.

[figure not shown]
3.4 Intervention Arm

Participating practices in the intervention arm will receive access to the clinical decision support system (CDSS) intervention in their primary care setting. The CDSS is an integrated management system that involves many facets of the healthcare system. It will focus on four key elements:

- 1) Translation of best-evidence to Primary Care Providers (PCP) through computerized decision support aids designed to enable PCP to handle the identification and rapid treatment of AF patients at the primary care level;
- 2) Engagement and empowerment of patients in the self-management of their disease;
- 3) Remote surveillance of AF patients through a range of data streams with proactive response to critical trends and situations;
- 4) Leveraging innovative health informatics and computer science technologies to develop an integrated knowledge-centric patient-centered disease management platform (DMP).

Interventions most frequently cited as efficacious to improve care and outcomes in disease management include: stakeholder education and reminders of best care practices; financial incentives to follow best practices; and, regular measurement and feedback of actual practices and outcomes [101]. In the successful ICONS project, financial incentives were not used; instead, a combination of education, reminders and repeated measurement and feedback communication of practices and outcomes were all employed, including the sharing of region-specific and sub-group data [103-106].

Figure 5. Study Flow Diagram

CONFIDENTIAL

Over the 5-year course of ICONS, it became evident that the network, itself, was also a likely efficacious intervention [104, 106]. Recent, basic science data support the observations and hypotheses generated by ICONS [112,113]. Briefly, this evidence suggests human behaviours are spread via networks of social contact, which add value by facilitation and reinforcement of beneficial behaviours. A few characteristics appear to be of key importance in relation to effectiveness. One is the number of reinforcing messages required to foster uptake of new behaviours, which will differ between individuals. This appears to be more important than who is delivering the message. Another is that the structure of the network also determines the extent and speed of behaviour adoption [113]. In this latter regard, the so-called clustered lattice network structure, which resembles the community-based organisation of ICONS, and is proposed for IMPACT-AF, is more efficient, or efficacious, than more random network structures [113].

For IMPACT-AF, we propose a broad community-based network of overlapping and shared interactions among providers, patients, their families and community-based referral services, all communicating with academic partners, patient advocacy organizations and policy makers in a clustered lattice type of network model integrated through a formalized electronic web. Such a network will facilitate the specific interventions outlined in Table 1 to overcome perceived impediments to optimal care.

Education will be provided to AF patients via the study website and paper-based materials included in patient mail outs.-Similar to what was offered in ICONS, [101,103] stakeholder education will be offered via patient advocacy organizations, an IMPACT-AF Newsletter, web site and bi-annual meetings.

The academic hospital-based specialized clinic is planned to serve as an additional, albeit non-randomized comparator, of care. Indeed, it is hypothesized that the management and outcomes of community-based patients in the intervention arm of the IMPACT-AF study will not only be superior to what is seen in the usual care arm, but it will be as good as the care provided for those patients being managed uniformly through the specialized AF clinic.

Table 1. Barriers to optimal care and core interventions

Identified barriers	Interventions
Lack of knowledge	Interactive education sessions
Perception/reality mismatch	Audit and feedback
Lack of motivation	Network reinforcement
Beliefs/attitudes	Peer influence / opinion leaders
Systems of care	Process design

3.4.1 Proposed Technology Framework

This research program involves systemic integration of advance health informatics technologies, best evidence, health models and knowledge translation strategies and best evidence to develop a technology-assisted Atrial Fibrillation (AF) management framework. The project will adopt a knowledge management approach to both develop and deploy the proposed clinical decision support framework. The proposed research encompasses a patient-centered care delivery paradigm, targeting both patients and primary care physicians (PCP) that leverages state-of-the-art computer technologies to design personalized, interactive, pre-emptive, socially cognizant, contextually-aware, evidence-based AF strategies delivered through electronic media. A patient-centered approach to the translation of evidence into practice will be taken, addressing the knowledge gaps of PCP and the engagement of AF patients to develop a patient centered program of research and care delivery for the management of AF.

Our intent is to develop a four-layered research and care delivery program to address Atrial Fibrillation management as a longitudinal care process. The clinical care layer will investigate the theoretical framework of the Expanded Chronic Care Model to develop, implement and integrate innovative models of evidence-based patient care regarding Atrial Fibrillation into clinical practice. This model is well suited to this program because of the persistent nature of arrhythmic and thromboembolic issues over a lifetime and the link between AF and underlying chronic diseases such as chronic heart failure [114]. The patient engagement layer will investigate commitment and empowerment models (Social Cognition Theory, Health Belief Model and Shared Decision Making Model) to develop a high-level patient engagement model that can help us understand and establish patient perceptions on AF management in terms of personal goals, environmental, behavioural, functional and economic factors. The knowledge translation layer will build on the synergy of integrated knowledge translation models with web technologies to develop a collaborative, ubiquitous and immersive knowledge translation, sharing and training environment for PCP. The knowledge-modeling layer aims to leverage knowledge management methodologies to achieve the transformation and translation of paper-based clinical guidelines into knowledge-driven clinical decision support systems.

From an E-health research perspective, we will pursue the following research components:

1. Healthcare Knowledge Modeling

Healthcare knowledge modeling involves the abstraction and representation of medical concepts, relationships, constraints and rules to realize a formal computable knowledge model defining the domain [115, 116]. The model will be generic, scalable, robust and flexible and will serve as a generic logical and executable template for the computerization of multiple co-morbid guidelines in addition to AF guideline. Cutting edge Semantic Web technologies such as highly expressive and computer interpretable OWL-Web Ontology Language [117] will be used to model the health care knowledge as Ontology.

The model will be based on three different, yet interrelated knowledge objects as follows: (a) Clinical knowledge about AF management encapsulated within evidence-based clinical guidelines; (b) Behavior change strategies that are represented in terms of health behavior models—such as social cognition, health belief, shared decision making and so on; and (c) Clinical workflows that capture the function and operational workings of healthcare institutions, eliciting the processes, decisional choices and resources. These three unique knowledge objects will be modeled as three independent ontologies—namely the AF Knowledge Ontology, Behavior Strategy Ontology and Care Workflow Ontology—yet their active interplay based on our existing knowledge morphing method [118] will align these ontologies to renders a holistic knowledge base that will be used for AF decision support purposes.

2. Clinical Decision Support System for Primary Care Providers

Healthcare knowledge modeled in terms of specialized ontologies can be executed through CDSS to provide case-specific decision support [119,120]. In this project, we propose to build on our existing research covering the development of ontology-driven CDSS using Semantic Web Technologies [117,121] to develop a guideline-mediated AF CDSS to assist family physicians to manage patients with AF. Our approach is to leverage state-of-the-art Semantic Web technologies [117] that provide methods to systematically translate ontologically-modeled medical knowledge into point-of-care interventions. We will use a logic-based knowledge morphing method to integrate the different ontologies, explicating the domain and process-specific decision logic, conceptual constructs, process workflows and constraints in terms of explicit logical rules. We will employ OWL-based reasoning methods, using logic-based proof engines, to infer guideline-mediated patient-specific diagnostic and therapeutic recommendation based on specific patient information provided by the physician. The novelty of our decision support approach is that PCP can request justifications and explanations for the recommendations suggested by the CDSS. The AF CDSS will be accessible through a secure web portal over the internet (with potential for a mobile app).

3. Patient AF Self-Management Aids

This research program aims to deliver personalized, proactive and pervasive AF self-management and monitoring aids to help with self-management via health behavior change. In this regard, we propose to develop a mobile app – called AF Care Partner – that will feature a range of patient-specific AF self-management aids as follows:

1. AF self-management plan adherence through (a) AF management goal setting and strategy design; (b) delivery of motivational, behaviour modification and emotion management educational messages; (c) vitals, diet, exercise, stress and mood recording diaries; (d) plan related alerts and reminders.

[figure not shown]
CONFIDENTIAL

2. AF self-management plan monitoring through (a) weekly progress reports reflecting on goal attainment; (b) daily and weekly trends of risk factors based on diary data; (c) observed risk related alerts; (d) mood/stress related alerts.
3. Communication with care providers, with potential for peer support. Patients will be able to access the app through smart phones and tablets.

The project's deliverable will be a robust, scalable and flexible clinical decision support framework (Figure 6) for managing AF with a suite of enabling health informatics services. The short-term goal is to develop and implement care pathways for managing AF based on best evidence in primary care settings. This component will be designed prior to patient enrollment, with end-user testing of functionalities prior to the start of the clinical trial. The long-term goal is to extend design and functionality of the framework in order to incorporate and streamline patient-specific care pathways for multiple co-morbid diseases that commonly occur with AF. Once implemented, such a framework will be able to provide evidence-based decision support services for a wide range of co-morbid scenarios that are deemed treatable in the primary care setting. The project will impact health outcomes in terms of improving evidence-based care delivery, patient safety and satisfaction, care quality, patient-centeredness and cost / resource-effectiveness.

Anticipated challenges include: (a) Adoption of the intervention by Primary Care Providers (PCP); (b) Privacy and security of patient information that is collected and managed by the clinical decision support system; (c) Recruitment of PCP across the rural and urban regions of Nova Scotia; and, (d) Integration of the clinical decision support system with existing health IT systems.

Figure 6. CDSS Visual.

3.4.2 Other Interventions

A Change Management plan may be developed and deployed to ensure the technical solution (CDSS) is embraced, adopted and utilized effectively by providers and patients, so that the intended benefits (improved patient outcomes and enhanced patient and provider satisfaction) can be realized.

CONFIDENTIAL

As per the Prosci® Change Management Process and ADKAR® Model, the 3 Phases of change will be addressed: Preparing for change, Managing Change and Reinforcing change™. Example activities would include: implementation of a readiness assessment, creation of a sponsorship model, change management plans developed to address ADKAR (Awareness, Desire, Knowledge, Ability and Reinforcement™) including plans for: Communication, Coaching, Training, Sponsor Roadmap and Resistance Management. Feedback would be collected and analyzed in order to diagnose gaps and or manage resistance. As necessary, corrective actions would be deployed and successes celebrated. (Prosci®, ADKAR®, Preparing for change, Managing Change and Reinforcing change™ are trademarks of Prosci Inc. 2012).

3.5 Contamination and Co-intervention

Contamination of the usual care arm will be limited by having separate investigator meetings for PCPs enrolled into each arm. Discussion amongst PCPs that may occur outside of study meetings will not be able to be monitored, however this type of contamination is unlikely to have a significant impact on the usual care arm as they will not have access to the CDSS.

3.6 Sources of Bias

In cluster-randomized trials, there are important sources of bias to consider: recruitment bias, baseline imbalance and loss of clusters [122]. Recruitment bias should be limited as all patients in each PCP practice will be included, thereby minimizing bias in types of AF patients. Baseline imbalance is unlikely to be an issue as there are a large number of clusters in this study. Loss of clusters is possible but unlikely since there is little migration of PCPs from Nova Scotia; thus, loss of an entire cluster over the period of follow-up is improbable.

3.7 Study Procedures

3.7.1 Randomization

Primary care centres will obtain their randomized assignment (intervention versus control) at the time of recruitment. (See Section 4.0 for Study Recruitment Procedures.) Randomization will be stratified by whether the PCP is urban or rural. Urban is defined as a population $\geq 10,000$, while rural is defined as $< 10,000$ population [123].

3.7.2 Treatment Period and Follow-up

The study will recruit PCPs until the goal of 200 is achieved, then follow patients for a minimum of 12 months. The intervention will be set up with appropriate training in the PCP practice prior to testing the intervention. There are no specific study visits for this trial; however, any unplanned PCP visits, emergency department visits and hospitalizations will be examined for important data (See Table 2).

3.7.3 Data Collection

Once informed consent has been obtained by the patient's PCP, a process to record retrospective baseline and ongoing clinical data prospectively will be implemented. Patients will be also requested to complete a patient case report form and quality of life questionnaire (either paper-based or electronic format) to gather relevant demographic and socioeconomic data.

Acknowledging the age profile of AF patients in NS, it is anticipated that a proportion of

CONFIDENTIAL

participants will chose not to complete online surveys or interact with the web-based tool. Completion of the web-based survey tools and / or interacting with the web-based tool, the AF Care Partner, is not mandatory for participation; all survey tools will be available to participants in a paper-based format.

In both study arms, baseline clinical data will be captured from the patient's chart by a data abstractor via on-site visit(s). Abstractors will utilize a laptop computer or tablet to record and transmit study data to secure and password protected servers located behind a firewall at Health Information Technology Services Nova Scotia (HITS-NS). This process will be repeated at 12 months for follow-up data collection in both study arms. Follow-up data for the intervention arm will also be captured through examination of data gathered during use of the CDSS.

The majority of patients at the start of the study are expected to have a past diagnosis of AF. As the study progresses, newly diagnosed patients are anticipated to be enrolled.

Review of PCP records will be done at 12 months to ensure completeness of outcome events. Clinical event / outcomes data will also be captured via review of hospitalization records for consented patients. Patients visiting the AF clinic in Halifax will be consented and data captured during their clinic visit. See Section 4.2 for further details.

Information to be collected on all patients will include contact details, demographic and socioeconomic characteristics, and, clinical, process of care and health outcome variables such as: Name, year and month of birth, health card number, mobile phone number, mailing address, internet access / smart-phone and social media usage, type of residence, gender, ethnicity, date of AF diagnosis, means of documentation of AF (ECG, Holter, other), medications, risk factors for AF, bleeding and stroke (based on HASBLED, CHADS2 and / or CHA2DS2-Vasc score), prior cardiovascular or other hospitalizations and ER / AF clinic / GP office visits for AF care, laboratory investigations (e.g., thyroid studies, renal function, hemoglobin, INR), referrals, alcohol use, smoking status, cardiac risk factors, other co-morbidities / past interventions and information on the patient's pharmacies of choice. Additional information that will be sought will relate to socioeconomic, quality of life and satisfaction with care (e.g., marital / employment status, annual household income, education level, care giver support, missed work, EQ-5D-5L questionnaire). See supporting data collection materials for a complete list of variables that will be captured from the patient and or the provider via Case Report / Data Collection Forms.

Table 2. Overview of variables collected during the study

Schedule Procedure	Initial Primary Care / AF Clinic Visit	Follow-up Visits	Tertiary Care (if applicable)
Visit date	X	X	X
Demographic data	X		
Medical history	X		
Investigations / Labs / Vital signs	X	X	X
Medications / Interventions	X	X	X
Socioeconomic / HRQoL	X	X	

CONFIDENTIAL

Events (including details)	X	X	X
----------------------------	---	---	---

Costs

The relevant costs for this study may include the cost associated with the development, implementation, and maintenance of the CDSS. All the health care resource utilization associated with managing and treating participating patients with AF will also be recorded. This health care resource utilization may occur in the participating primary care providers and the tertiary AF care clinic.

HRQoL

HRQoL will be measured using health utility, a single index anchored at 0 representing death and 1 representing full health. Health utilities can be used to calculate quality adjusted life year (QALY) for economic evaluation. The EQ-5D is a prominent example of the utility-based instruments, with some indication that it has become the most widely used multi-attribute instrument in the world [124]. It consists of 5 dimensions: mobility, self-care, usual activities, pain/discomfort, and anxiety/depression. Each dimension defines 3 levels indicating no problems (level 1), some problems (level 2), and extreme problems (level 3)(referred to as EQ-5D-3L) [123]. A new version of the EQ-5D has recently developed by refining the response options of the EQ-5D-3L to reflect 5 levels of impairment: no, slight, moderate, severe, and extreme problems in the five dimensions (the EQ-5D-5L) [125]. The EQ-5D-5L tends to improve descriptive richness and discriminatory power as it defines a total of 3125 health states compared to only 243 by the EQ-5D-3L. The EQ-5D-5L will be used in our study.

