3.0 STUDY DESIGN

3.1 Description

The proposed project falls into the scope of what has been termed a pragmatic or practical clinical trial [109-111]. This means that the hypothesis and study design have been developed specifically to answer questions faced by policy makers as they seek to develop new and effective population health management approaches. The first goal is to develop a CDSS that has undergone preliminary assessment of its clinical usefulness by knowledge opinion leaders as well as practical field-testing of its utility and dependability in practice settings. Following this, a rigorous analytical assessment of efficacy will be undertaken.

Specifically, IMPACT-AF will include a prospective, randomized, unblinded cluster design clinical trial, proposed to take place within Nova Scotia over the time period of 2014-2018, that will investigate whether a Clinical Decision Support System (CDSS) improves the clinical outcomes of patients with AF. Primary care providers (n=200) will be randomized to usual care versus use of the CDSS in a 1:1 fashion, at the level of the clinic practice. In order to facilitate the study, primary care providers will be required to have high speed internet access. The study will follow patients over a minimum of 12 months after enrolment.

Patients Included in the Analysis:

1. Age \geq 18 years
2. Electrocardiographically confirmed atrial fibrillation or documentation of past diagnosis or management of AF in the patient's medical record
3. Able to provide informed consent in English
4. Resident of Nova Scotia

Exclusion Criteria:

1. Patients unable to provide informed consent
2. Patients who have a terminal illness and are not expected to be alive at the end of follow up.

3.2 Study Flow:

See Figure 5 for a Summary of Study Flow.

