Once eligible patients are identified, a consent brochure will be mailed or handed to the patient. If the patient is seen in the provider's office, consent will be sought at the time of visit. Each patient will be assigned a study number for coding purposes; otherwise, unique identifiers for health record identification and linkage will remain with the health facility at which they were recruited and where their AF care is routinely provided. This affords a mechanism to allow follow-up on long-term care procedure and events through subsequent chart review or database linkage without having to include unique health identifiers in the IMPACT-AF study registry.

AF Clinic ID / Recruitment: Patients visiting the AF Clinic at the QEII Health Science Centre will also be asked to participate and sign a consent form. The patient's primary care provider would be notified that the patient has agreed to participate via the AF clinic site.

Inclusion Criteria:

Primary Care: All new and previously diagnosed patients ≥ 18 years of age with AF and a life expectancy > 12 months will be eligible for study enrollment. In addition, patients will need to be:

- A registered and regular patient at a primary care practice participating in the IMPACT-AF study;
- Able to read, understand and communicate in English.
- A resident of Nova Scotia.

Patients in the Intervention Arm will have the option to interact with the CDSS through the patient portal, the AF Care Partner tool. These patients will therefore need access to the Internet and be willing to input information and receive feedback and reminders from the AF Care Partner tool over the duration of the study. Patients can revoke their AF Care Partner tool participation if desired.

CONFIDENTIAL

All AF Clinic (QEII HSC) patients will be invited to participate in the IMPACT-AF study by signing an informed consent form.

Exclusion Criteria: Patients with a terminal illness (expected death within 12-months) and those having cognitive impairment or who are unable to communicate in English will be considered ineligible for participation. Also ineligible for inclusion are AF patients whose care is being significantly overseen by a specialist as well as those who are patients of the hospital-based AF clinic at the QEII Health Sciences Centre.

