- One or more District Health Authority representatives
- Other participants may be added e.g. NSCAD.

Advisory Members are expected to: actively participate in committee meetings; respect confidentiality of all information discussed, as appropriate; serve for the duration of the project, but may resign by providing the Committee Chair with written notice two months in advance of the effective date of their resignation. Each member has one vote on committee decisions. The quorum for all meetings shall consist of a majority of the voting members in attendance. Committee expenses / honoraria, if applicable, are provided from within the project budget.

- Mandate: Concerned with project development, providing input, guidance and direction on the project, its goals, implementation and any major policy issues / decisions. Responsible for promoting and driving the project in their organizations and across the province.
- Meetings twice yearly.
- Meeting minutes will serve as record of Committee activities to be distributed within 30 days / months following each meeting.
- Administrative support provided by the Project Office.

5.5.3 Adjudication Committee:

An adjudication committee may be created to provide oversight regarding adjudication of certain study outcomes. Anticipated members include: a clinical cardiologist, an electrophysiologist, a neurologist and a haematologist. The committee will be blinded to

treatment allocation if applicable. Meetings will be held as needed subsequent to the collection of data.

5.5.4 External Review Committee:

An external review committee of 4-5 participants may be created to provide visionary oversight and peer-review on a yearly basis. Consideration will be given to non-Nova Scotia, non-Canadian participants. Representatives are likely to include computer scientists, clinical experts, knowledge translation researchers, health services researchers, and health policy makers or researchers.

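### CDSS data are an extra follow-up source in the intervention arm only, and nothing in the text reviewed keeps CDSS-only findings out of the outcome comparison

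*Protocol*

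**What the plan says.** Protocol 3.7.3 has a data abstractor take baseline data from the chart in both arms, and then: "This process will be repeated at 12 months for follow-up data collection in both study arms". The next sentence adds a source for one arm: "Follow-up data for the intervention arm will also be captured through examination of data gathered during use of the CDSS".

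Later in the same section two event sources are named, neither restricted by arm: "Review of PCP records will be done at 12 months to ensure completeness of outcome events" and "Clinical event / outcomes data will also be captured via review of hospitalization records for consented patients". Section 3.7.2 also says that ED visits and hospitalizations will be examined, but 3.7.3 names no ED record source.

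Control practices cannot supply the extra source. Section 3.5 says of the usual care arm that "they will not have access to the CDSS". Patient-entered data are likewise one-sided: "Patients in the Intervention Arm will have the option to interact with the CDSS through the patient portal, the AF Care Partner tool" (4.2).

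The trial is a "prospective, randomized, unblinded cluster design clinical trial" (3.1). Section 3.6 considers recruitment bias, baseline imbalance and loss of clusters, but not unequal ascertainment of outcomes. The main text of the SAP does not say which records the outcomes come from. It refers to Appendix 1 for outcome definitions, and that appendix was not in the text reviewed.

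**The concern.** A comparison between arms needs outcomes that were looked for in the same way in each arm. Under 3.7.3 an event, prescription or referral that appears only in the CDSS can enter the follow-up data of an intervention patient. The same occurrence in a control patient has no such route.

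The direction depends on the outcome:

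- **Events** (the primary composite and bleeding): extra capture in the CDSS arm adds events there. It makes the intervention look worse and costs power.
- **Care processes** (anticoagulant appropriateness, specialist access, echocardiography): extra capture credits the CDSS arm with care that may have been given equally, but recorded less fully, under usual care. It makes the intervention look better.

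The exposure is uneven. Overnight cardiovascular admissions should appear in hospitalization records whatever the arm. An AF-related ED visit without admission is part of the primary composite and need not appear there. It may depend on primary care records, and the CDSS supplements those in one arm only.

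**Working it through.** **1. Is the source one-sided, and does anything neutralise it?**

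| Source | CDSS arm | Usual care | Where |
|---|---|---|---|
| Chart abstraction at 12 months | yes | yes | Protocol 3.7.3 |
| Primary care record review at 12 months | yes | yes | Protocol 3.7.3 |
| Hospitalization record review | yes | yes | Protocol 3.7.3 |
| Data gathered through CDSS use | yes | no | Protocol 3.7.3, 3.5 |

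I looked for text that limits CDSS data to describing use, requires confirmation in a common source, or plans an analysis on common sources only. The text reviewed has none of these. The SAP's analysis with groups coded X and Y masks the analyst but does not affect how data are captured.

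**2. The plan's own figure.** Inputs from Protocol 3.8: control 0.50, intervention 0.40, two-sided alpha 0.05, power 80%, ICC 0.05, cluster size 9.

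- n per arm = (1.96 + 0.84)² × [0.5×0.5 + 0.4×0.6] / 0.10² = 7.84 × 0.49 / 0.01 = 384.16; total 768.32
- Variance inflation = 1 + (9 − 1) × 0.05 = 1.4
- 768.32 × 1.4 = 1075.65, which matches the Table 3 row.

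Effective patients per arm = 537 / 1.4 = 383.6. The usual two-proportion test then has 79.6% power for 0.50 versus 0.40.

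**3. Illustration of unequal capture.** The documents give no capture rates, so 90% and 95% are assumptions. Observed proportion = true proportion × capture. Power = Φ[(|d| − 1.96·SE₀)/SE₁], where d is the observed difference, SE₀ is pooled and SE₁ unpooled, with 383.6 patients per arm.

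| Truth | Capture, control / CDSS | Observed, control / CDSS | Difference | Result |
|---|---|---|---|---|
| 50% / 40% | 90% / 90% | 45.0% / 36.0% | 9.0 points (RRR 20%) | power 72.0% |
| 50% / 40% | 90% / 95% | 45.0% / 38.0% | 7.0 points (RRR 15.6%) | power 50.3% |
| 50% / 50% | 90% / 90% | 45.0% / 45.0% | 0 | rejection 5.0% |
| 50% / 50% | 90% / 95% | 45.0% / 47.5% | 2.5-point false excess in CDSS arm | rejection 10.7% |

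For the second row, SE₁ = √[(0.45×0.55 + 0.38×0.62)/383.6] = 0.0355 and SE₀ = √[2 × 0.415 × 0.585/383.6] = 0.0356. Power is therefore Φ[(0.07 − 0.0697)/0.0355], about 50%.

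Equal under-capture lowers power (79.6% to 72.0%) but leaves the relative risk reduction at 20% and the type I error at 5%. Unequal capture is what distorts the estimate. Each extra point of capture in the CDSS arm moves the difference by 0.4 points if its true rate is 40%, or 0.5 points if it is 50%.

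These figures use the patient proportions of Protocol 3.8. The SAP's primary analysis treats the outcome as a number of events and reports a hazard ratio, so they do not carry over to it directly.

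**The case against.** The strongest reply is that the protocol nowhere says CDSS data decide outcomes. The sentence concerns follow-up data in general, and the same section names event sources that apply to both arms. A reader might infer that biased outcome capture is built into the plan. The documents do not support that: they permit it and do not exclude it. This part of the reply stands, and the point is a missing rule rather than a demonstrated bias.

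The route for CDSS-only findings may also be narrow. Provider entries come from the practice whose charts are reviewed. The patient tool is optional, and the diaries listed in 3.4.1 cover vital signs, diet, exercise, stress and mood rather than ED visits. Electrophysiology services are centralised at one hospital (Protocol 1.3), so ablation is less exposed. This narrows the point to the outcomes listed under the verdict. It does not remove it, because 3.7.3 expressly treats the CDSS as an added source and 3.4 describes remote surveillance through several data streams.

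Two further inferences should be resisted. The first is that the optional adjudication committee (5.5.3) is part of this problem. Adjudication classifies events already found and would not remove extra detection. The second is that the damage could never be undone. That holds only if sources are pooled without a record of where each item came from, and the documents do not say that they will be.

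**Conclusion.** The point holds in limited form. The plan adds a follow-up source in one arm only, and the text reviewed has no rule that keeps CDSS-only findings out of the comparison. SAP Appendix 1 might contain such a rule.

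Most exposed are ED visits without admission, bleeding not leading to admission, anticoagulant appropriateness, referrals and echocardiography. Overnight cardiovascular admissions are probably little affected, and it would be wrong to read the concern as applying to them equally.

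On the primary and bleeding outcomes the bias from extra capture runs against the intervention, so it would not create a false claim of benefit there. Bias in its favour is confined to process and treatment outcomes, all secondary.

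The size is unknown and could be near zero. The range of 0 to 2.5 spurious points, and of 72% down to about 50% power, rests wholly on assumed capture of 90% in control and 90% to 95% in the CDSS arm. It is not an estimate for this trial. The change is worth making because it is cheap and protects the comparison whatever the true gap.

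**What to change.** In Protocol 3.7.3 and the SAP, state that:

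- the primary, safety, clinical and process outcomes are built only from sources available in both arms: 12-month chart and primary care record abstraction, hospitalization and ED records, and the same questionnaires;
- CDSS data are used only to describe CDSS use, or in a labelled sensitivity analysis that adds CDSS-only findings;
- the source of each event is recorded, so that CDSS-only items can be separated.

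ED records should be named explicitly, since 3.7.2 says ED visits will be examined while 3.7.3 names only hospitalization records.

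The cost is a few sentences and a source field for each event. If ED records were not already to be obtained in both arms, access to them would be additional work. A few events seen only in the CDSS would be left out of the main analysis. One limitation remains: if using the CDSS changes what providers write in the chart, restricting to common sources does not remove that effect.
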